## 8.3. Patient Withdrawal Criteria

For all patients, it is the intent that patients who discontinue study medication (at any time) for any reason will continue to be followed for all protocol-planned study visits through the completion of the 24-week treatment period, and will have all endpoints (including efficacy) collected accordingly.

The Investigator, Sponsor, or its designee may decide a patient should discontinue treatment at any time and for any reason. In addition, patients will discontinue randomized treatment if they:

- Experience an intolerable adverse event: such events include, but are not limited to, adverse events ≥ Grade 4\*, bone marrow-related events, a ≥ Grade 3\* cardiac event (\*CTCAE v5.0 criteria);
- Require a medication that is prohibited by the protocol. However, under certain circumstances, and in consultation with the Medical Monitor, short-term use of a prohibited medication may not necessitate withdrawal of treatment when its use is unlikely to unfavorably alter the risk-benefit of subject participation;
- In the opinion of the Investigator, have any medically appropriate reason;
- Become pregnant;
- Have a serious adverse event associated with a SARS-CoV-2 infection;
- The Investigator believes that further treatment is undesirable or the risk-benefit profile has become unfavorable.

Furthermore, dose interruptions lasting more than 21 days may require treatment discontinuation on a case by case basis following consultation with the Medical Monitor.

In addition, patients are free to withdraw from participation in the study at any time, for any reason, and without prejudice. The Investigator must withdraw any patient from the study if the patient withdraws consent and requests to stop participating in the study. Patients who withdraw or are withdrawn from the study will not be replaced.

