## 9.2.1. Dose Interruption Safety Criteria and Management

Patients who experience hematologic adverse events as described in Table 3, significant clinical laboratory abnormality, or adverse events that may reflect an unfavorable risk-benefit profile may have their dose interrupted at the discretion of the Investigator. The Medical Monitor(s) should be consulted whenever possible prior to decisions for dose interruption.

Patients who withdraw consent and therefore are discontinued from the study should undergo an Early Termination Visit and subsequent Safety Follow-up Visit as appropriate per Section 8.3.1 Patient Withdrawal Procedures, and associated adverse events followed as described in Section 11 Adverse Events.

Hematology parameters will be assessed bi-weekly for the first 4 weeks of the Treatment Period, and every 4 weeks thereafter for the remainder of the study. Prior to dose interruption, hematology parameters should be confirmed with repeat testing at an Unscheduled Visit within 72 hours, except in severe cases (i.e.: neutrophil counts below 0.5 x 10^9/L) where immediate interruption of dosing is necessary for the safety of the patient. **Blood draws confirming dose interruption criteria should occur prior to the first daily dose on the day of draw.** 

Dose interruption requirements for hematologic abnormalities are provided below. However, less significant changes may warrant clinical intervention and the Investigator should use his/her best clinical judgment when considering a dose interruption whether for singular or aggregate hematology results above the limits provided in Table 3, or for other clinical signs, symptoms, or considerations that suggest dose interruption is in the best interest of the patient.

Table 3: Selected Hematologic Thresholds for Dose Interruption

| Neutrophil Count                             | Dose Adjustment  |
|--|--|
| Between 0.5 to 1 x 10  /L        | Interrupt dose until recovered to greater than 1.5 x 10  /L and  |
| (Grade 3)                                    | resume dosing at previous dose   |
| Less than 0.5 x 10  /L (Grade 4) | Severe case: Interrupt dose immediately and repeat CBC with differential within 72 hours. Recommend hematology consult and contact medical monitor. Permanent discontinuation of treatment should occur upon repeat confirmation of value |
| Female Hemoglobin Level                      | Dose Adjustment  |

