| Less than 10 g/dL                            | Interrupt dose until recovered to greater than 10.5 g/dL and resume dosing at previous dose  |
| Male Hemoglobin Level                        | Dose Adjustment  |
| Less than 11.5 g/dL                          | Interrupt dose until recovered to greater than 12 g/dL and resume dosing at previous dose  |
| Platelet Count                               | Dose Adjustment  |
| Less than 75 x 10  /L            | Interrupt dose until recovered to greater than 100 x 10  /L and resume dosing at previous dose   |
| Greater than 750 x 10  /L        | Interrupt dose until recovered to less than 600 x 10  /L and resume dosing as prescribed by the Investigator   |

Upon dose interruption, the parameters that triggered the interruption should be monitored at least weekly until either: 1) recovery above the threshold for dosing resumption is achieved, or 2) a 21-day dose interruption period has elapsed, at which time a discussion between the PI and the Medical Monitor should occur to evaluate whether or not the subject should discontinue treatment permanently. In the case of severe neutropenia (neutrophil counts less than 0.5 x  $10^9/L$ ) patient should interrupt dose **immediately** and repeat CBC with differential within 72 hours. The Medical Monitor should be contacted and a hematology consult should be made if appropriate. Permanent discontinuation of treatment should occur upon repeat confirmation of value. Patients who discontinue treatment due to lack of acceptable recovery of parameters should continue to be followed for all safety and efficacy assessments through the completion of the 24-week treatment period, and will have all endpoints (including efficacy) collected accordingly.

Subjects with both a positive SARS-CoV-2 test (antigen or antibody) AND signs or symptoms consistent with SARS-CoV-2 infection should immediately interrupt dosing with study drug. Dose interruption should continue until symptoms subside (it is not necessary to have a negative SARS-CoV-2 test result). If symptoms do not subside within a 21-day dose interruption period, a discussion between the PI and the Medical Monitor should occur to evaluate whether or not the

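### Section 8.3 requires study drug to stop for any adverse event of Grade 4 or higher, but the hemoglobin and low-platelet rows of Table 3 restart it at the previous dose after recovery, and neither document says which rule prevails

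*Protocol*

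**What the plan says.** Protocol Section 8.3 introduces its list of stopping criteria with "In addition, patients will discontinue randomized treatment if they". The first criterion is "Experience an intolerable adverse event: such events include, but are not limited to, adverse events ≥ Grade 4", graded by CTCAE v5.0. It makes no exception for hematology values.

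Section 9.2.1 covers the same ground by parameter. It opens with "Patients who experience hematologic adverse events as described in Table 3", who may have dosing interrupted at the Investigator's discretion. It then introduces Table 3 with "Dose interruption requirements for hematologic abnormalities are provided below". The rows that matter here are:

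- Female hemoglobin below 10 g/dL: "Interrupt dose until recovered to greater than 10.5 g/dL and resume dosing at previous dose".
- Male hemoglobin below 11.5 g/dL: "Interrupt dose until recovered to greater than 12 g/dL and resume dosing at previous dose".
- Platelets below 75 x 10^9/L: "Interrupt dose until recovered to greater than 100 x 10" to the ninth per litre, then resume at the previous dose.

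Only the neutrophil rows are split by grade. For counts below 0.5 x 10^9/L, labelled Grade 4, the table calls for immediate interruption and a repeat count within 72 hours, and adds "Recommend hematology consult and contact medical monitor. Permanent discontinuation of treatment should occur upon repeat confirmation of value".

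**The concern.** Both sections are written as instructions to sites, and they give opposite final actions for the same patient. A site working from Table 3 would give the full previous dose again to a patient whom Section 8.3 says must stop. A site working from Section 8.3 would not. Identical events could then be handled differently across the roughly 50 planned sites.

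The layout of Table 3 makes the first outcome plausible. Because it spells out a Grade 4 stop for neutrophils alone, a reader can reasonably infer that the other parameters have none.

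Handling also determines where an event is reported. Protocol Section 12.4.8 and SAP Section 9.3 tabulate adverse events leading to discontinuation separately from those leading to interruption. Protocol Section 8.5 lists a high frequency of either as a possible trigger for an unscheduled DMC review.

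**Working it through.** There is no figure in the plan to reproduce. The check is textual, with a simple row count.

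**1. Table 3, row by row**

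| Parameter and entry threshold | Grade 4 tier? | Action after recovery or repeat |
|---|---|---|
| Neutrophils 0.5 to 1 x 10^9/L | This is the Grade 3 tier | Previous dose once above 1.5 x 10^9/L |
| Neutrophils below 0.5 x 10^9/L | Yes | Permanent stop if the repeat confirms |
| Female hemoglobin below 10 g/dL | No | Previous dose once above 10.5 g/dL |
| Male hemoglobin below 11.5 g/dL | No | Previous dose once above 12 g/dL |
| Platelets below 75 x 10^9/L | No | Previous dose once above 100 x 10^9/L |
| Platelets above 750 x 10^9/L | No | Once below 600 x 10^9/L, as the Investigator prescribes |

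- All rows: 2 neutrophil + 2 hemoglobin + 2 platelet = 6.
- Low-count rows: 6 − 1 (high platelets) = 5.
- Low-count rows with no lower bound, no Grade 4 tier and a restart at the previous dose: 5 − 2 (neutrophils) = 3.
- Low-count parameters with no Grade 4 tier: hemoglobin and platelets, 2 of 3.

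**2. Do both rules reach the same event?** Yes, on the protocol's own definitions.

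- Section 9.2.1 itself calls the Table 3 findings adverse events.
- Section 11.1 counts a laboratory abnormality as an adverse event if the Investigator judges it important enough to need dose interruption.
- Section 11.2.2 applies CTCAE v5.0 to the grading of all events.
- The three rows have no lower bound, so they cover the most severe values as well as the mild ones.

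**3. An example.** A platelet event is graded 4. Dosing is interrupted and the count rises above 100 x 10^9/L within 21 days.

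- Section 8.3: randomized treatment is discontinued.
- Table 3: dosing resumes at the previous dose.
- The discussion with the Medical Monitor that Section 9.2.1 sets at 21 days without recovery is never reached, because the count recovered.

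**4. Is there text that settles it?**

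- Section 7.1 says cytopenias are managed according to severity, by interruption or by discontinuation. This is compatible with 8.3 prevailing but sets no order.
- Section 9.2 leaves interruption or discontinuation to the Investigator in consultation with the Medical Monitor. It does not refer to grade.
- Section 9.2.1 asks for Medical Monitor contact, where possible, before interrupting. Nothing is tied to restarting.
- Section 10.13 asks for discussion of significant hematologic abnormalities in general.
- The 21-day provisions in 8.3 and 9.2.1 concern duration, not grade.
- SAP Section 2 gives the SAP primacy over the protocol for analyses only.

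No statement of precedence was found in either document.

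**5. Does it reach the primary analysis?** No. Section 8.3 intends patients who stop drug to be followed to Week 24 with all endpoints collected. Section 12.4.2 uses a treatment-policy strategy for temporary and permanent discontinuation alike, and SAP Section 8.2.1 keeps SALT scores observed after discontinuation.

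**The case against.** The best defence is that the two sections fit together on an ordinary reading. Section 8.3 is mandatory. Table 3, by its title, gives selected thresholds for interrupting doses, so it need not be a complete stopping schedule. A patient already discontinued under 8.3 has no interrupted dose to resume. Section 9.2 brings in the Medical Monitor when the choice between interruption and discontinuation is made, which is where 8.3 would be applied. There are further safeguards:

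- Parameters are monitored at least weekly during interruption (9.2.1).
- A cytopenia meeting a seriousness criterion reaches the sponsor within 24 hours (11.6.1), and 11.2.1 names blood dyscrasias as an example of an important medical event.
- The sponsor may stop any patient's treatment at any time (8.3).
- A high frequency of Grade 3/4 events can prompt DMC review (8.5).

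Most of this stands. The overriding reading is available and the safeguards lower the risk. What remains is that no text states the override, 9.2.1 describes its table as requirements, and the Grade 4 stop given for neutrophils alone points the other way. Not every laboratory Grade 4 will meet a seriousness criterion either, since 11.1 separates severity grade from seriousness.

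Three stronger readings might be inferred, and the documents do not support them.

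- Table 3 does not send a patient back to full dose while still cytopenic. Each restart requires recovery to a stated threshold.
- Section 8.3 also lists bone marrow-related events with no grade limit, which might suggest that it cancels every low-count restart, including after Grade 3 neutropenia. The phrase is undefined, and Table 3 expressly allows that restart, so the text does not establish so wide a conflict.
- The conflict might be thought to bias the efficacy result. The treatment-policy strategy and continued follow-up rule that out as a claim.

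**Conclusion.** The concern holds as a conflict between two stated rules. A Grade 4 hemoglobin or low-platelet adverse event that recovers is a stop under Section 8.3 and a restart at the previous dose under Table 3. It touches 3 of 5 low-count rows and 2 of 3 low-count parameters. The consequence is possible re-exposure of a patient who should have stopped, and uneven handling between sites. The primary analysis, alpha and power are unaffected. It should be corrected, but it does not threaten the trial's conclusions.

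This rests on two assumptions. The first is that a Grade 4 event in these parameters lies below the Table 3 entry threshold. The documents give no CTCAE cut-offs for hemoglobin or platelets, but the rows are open-ended downwards. The second is that the Investigator records the abnormality as an adverse event, as 9.2.1 and 11.1 imply. With no cytopenia rates in the documents, the number of patients affected cannot be estimated; the row count describes the table, not the risk.

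**What to change.** Amend Section 9.2.1 and Table 3 as follows.

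1. State that the restart instructions in the female hemoglobin, male hemoglobin and low-platelet rows apply only to events below Grade 4 (CTCAE v5.0).
2. State that a hemoglobin or platelet adverse event of Grade 4 or higher leads to permanent discontinuation of study drug under Section 8.3, with follow-up to Week 24.
3. Confine this precedence to the Grade 4 criterion. A blanket clause that 8.3 prevails would bring in the ungraded bone marrow criterion and could cancel restarts after Grade 3 neutropenia. Those restarts, and the confirmed-repeat rule for Grade 4 neutropenia, should stay as they are.
4. State in Section 8.3 that bone marrow-related events do not include cytopenias below Grade 4 managed under Table 3.
5. If immediate interruption is also wanted for Grade 4 hemoglobin or platelet events, extend the exception to repeat testing in 9.2.1, which now names only neutrophils below 0.5 x 10^9/L. Otherwise the table and the text would disagree.

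A confirming repeat before permanent discontinuation for hemoglobin and platelets is not part of this proposal. Section 8.3 does not ask for one, and adding it would loosen the mandatory rule.

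The cost is a restriction on three rows and a few sentences, by protocol amendment. There is no SAP change, no extra patients and no extra scheduled visits. The downside is that patients who would have restarted after recovery stay off drug. They are probably few, but the documents give no rate.

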## **8.3.1.** Patient Withdrawal Procedures

If a patient withdraws consent from further participation in the study, the Investigator will record the reason(s) for early termination on the relevant electronic case report form (eCRF). The specific reason for the withdrawal should be carefully documented on the eCRF.

## 8.4. Emergency Unblinding of Treatment Assignment

In the case of a medical requirement to break the blind to determine appropriate treatment for an adverse event, unblinding of a patient's treatment assignment can be achieved through the study-specific Interactive Web Response System. If possible, the Investigator should discuss the circumstances with the Medical Monitor(s) prior to accessing unblinding information. In the event of a blind break, the Medical Monitor(s) will be notified through the electronic data capture system. The patient for whom the blind is broken should be subsequently withdrawn from the study. The details regarding the process of breaking the blind are outlined in the Medical Monitoring Plan and the Pharmacy Manual.

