Patient safety will be monitored throughout the trial by the Investigator and supported by regular review by the Medical Monitor and DMC. Chemistry and hematology laboratory values will be assessed under fasted conditions bi-weekly for the first month of the treatment period, followed by every 4 weeks through the remainder of the study. Lipid levels will be assessed every 4 weeks throughout the Treatment Period. In light of the COVID-19 pandemic, challenges in the conduct of study visits may arise from quarantines, site closures, and/or travel limitations. To ensure the safety of trial participants and to minimize risk to trial integrity, alternative methods for drug dispensation and assessments, including telemedicine visits and clinical laboratory blood draws at a local laboratory or via a Home Health Care agency, may be offered for those trial participants who may no longer have access to the investigational site. Significant cytopenias or other hematologic abnormalities will be managed by severity through dose interruption or discontinuation, and signs and symptoms of infection will be closely monitored and treated promptly. Patients who experience intolerable symptoms during treatment may discontinue treatment at the judgement of the Investigator, but will be followed for safety and efficacy assessments until Week 24, unless they withdraw consent. Patients may withdraw consent at any time.

Following the 24-week Treatment Period, patients will have the opportunity to continue receiving treatment in an Open-Label Extension study. If a patient does not wish to continue into the Open-label

Extension study, they will complete treatment at Week 24 and return in 4 weeks for the Post-Treatment Safety Follow-up to assess safety following treatment completion.

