Lipid levels will be assessed every 4 weeks throughout the Treatment Period. In light of the COVID-19 pandemic, challenges in the conduct of study visits may arise from quarantines, site closures, and/or travel limitations. To ensure the safety of trial participants and to minimize risk to trial integrity, alternative methods for drug dispensation and assessments, including telemedicine visits and clinical laboratory blood draws at a local laboratory or via a Home Health Care agency, may be offered for those trial participants who may no longer have access to the investigational site. Additional information will be documented in study manuals. Significant cytopenias or other hematologic abnormalities will be managed by severity through dose interruption or discontinuation, and signs and symptoms of infection will be closely monitored and treated promptly. Patients who experience intolerable symptoms during treatment may discontinue treatment at the judgement of the Investigator, but will continue in the study and complete all assessments unless they withdraw consent. Patients may withdraw consent at any time.

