## 7.3. Method of Treatment Assignment and Blinding

Patients will be randomized in a 1:2:1 ratio (12 mg BID:8 mg BID:placebo). Randomization will be stratified by scalp hair loss into one of the following two categories: 1) Partial scalp hair loss (SALT  $\geq$  50 and < 95); 2) Complete or near-complete scalp hair loss (SALT  $\geq$  95). The randomization schedule will be generated prior to study start.

All study patients, Investigators, and site study staff will be blinded to study drug assignment for the duration of the study. Tablets and packaging of CTP-543 and placebo will be identical in appearance.

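### Protocol 8.4 takes an unblinded patient out of the study, not only off study drug; this departs without a stated reason from the retention intent in 8.3 and creates avoidable missing Week 24 data

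*Protocol*

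**What the plan says.** Protocol 8.4 covers a blind broken out of medical need, to choose treatment for an adverse event. It ends: "The patient for whom the blind is broken should be subsequently withdrawn from the study". It gives no reason and says nothing about later visits. Only the mechanics of breaking the blind are referred elsewhere, to the Medical Monitoring Plan and the Pharmacy Manual.

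The retention text runs the other way:

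- Protocol 8.3 states as an intent, for all patients, that "patients who discontinue study medication (at any time) for any reason will continue to be followed for all protocol-planned study visits" to the end of the 24 weeks, with efficacy endpoints collected. It also says: "Patients who withdraw or are withdrawn from the study will not be replaced".
- The synopsis says of patients who stop for intolerable symptoms, "but will be followed for safety and efficacy assessments until Week 24, unless they withdraw consent".
- Protocol 7.1 says of the same patients, "but will continue in the study and complete all assessments unless they withdraw consent".
- Protocol 9.2.1 says that patients whose laboratory parameters do not recover "should continue to be followed for all safety and efficacy assessments through the completion of the 24-week treatment period".

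Protocol 12.4.2 applies a treatment policy strategy to stopping treatment, so Week 24 response counts whether or not the patient is still on drug. Neither document names unblinding as an intercurrent event or as a category of missing data. SAP section 13, which lists departures from the protocol, does not mention it.

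**The concern.** The protocol elsewhere separates leaving treatment from leaving the study. Section 8.3 lists triggers for stopping randomized treatment and makes study withdrawal mandatory only when consent is withdrawn. Section 8.4 attaches study withdrawal to a clinical event. Two patients with equally severe adverse events are then handled differently: the one who stops drug without unblinding is seen to Week 24, and the one who is unblinded is not.

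Most of what is lost is scheduled safety, laboratory and endpoint visits between the exit and Week 24, in patients selected because an adverse event was serious enough to need the treatment code. For the primary endpoint, Week 24 SALT becomes missing and has to be imputed, although the patient might have been willing to attend. The strategy in 12.4.2 is meant to limit exactly this kind of missing value.

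**Working it through.** **What happens to the data after an exit under 8.4**

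1. The patient stays in the Efficacy Population (randomized and dispensed drug) and is not replaced (8.3).
2. I take an Early Termination Visit and a Safety Follow-up Visit to apply from Protocol Table 2. The explicit instruction in 9.2.1 is narrower: "Patients who withdraw consent and therefore are discontinued from the study should undergo an Early Termination Visit and subsequent Safety Follow-up Visit".
3. SAP 8.1.2 reassigns early termination visits by analysis window. Week 24 SALT is therefore missing unless that visit falls on Days 166-172 (SAP Table 2, efficacy columns).
4. SAP 8.2.1 uses SALT after treatment discontinuation only for patients still on study. Otherwise the score is imputed as missing at random from the patient's own arm, given baseline and earlier SALT.
5. Sensitivity 1 (SAP 8.2.3) imputes exits for an adverse event from the control arm, but takes that reason from the sub-reasons under withdrawal of consent on the eCRF. A patient withdrawn by rule may not be captured there; the eCRF page is not available, so this stays open.
6. Sensitivity 2, the tipping-point analysis, adjusts every imputed value and so covers these patients.

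**The plan's own figure**

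Inputs from Protocol 12.1: response 40%, 26% and 9%; arms of 110 (12 mg), 220 (8 mg) and 110 (placebo); continuity-corrected chi-square; two-sided alpha 0.025.

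With x responders of n1, y of n2, N = n1 + n2 and s = x + y, the statistic is N(|x·n2 - y·n1| - N/2)² / [n1·n2·s·(N - s)]. Power is the sum of the binomial probabilities of all (x, y) that reject in favour of active drug.

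- 8 mg, 220 vs 110: 92.9% (stated: about 92%).
- 12 mg, 110 vs 110: 99.94% (stated: above 99%).

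The stated power reproduces.

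**Power if unblinded patients were dropped outright**

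At 3% per arm, 110 × 0.97 = 106.7, taken as 107, and 220 × 0.97 = 213.4, taken as 213.

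- 8 mg, 213 vs 107: 92.2%.
- 12 mg, 107 vs 107: 99.93%.

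This is harsher than the plan, because multiple imputation keeps these patients in the analysis.

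**Effect on the estimate**

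The documents give no unblinding rate. The rate r = 0.5-3% below is an assumption, equal to 440 × r = 2.2 to 13.2 patients.

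- Largest shift in an arm's rate from one patient: 1/110 = 0.91 points (12 mg or placebo); 1/220 = 0.45 points (8 mg).
- One true non-responder imputed at the planning rate: 0.40/110 = 0.36 points (12 mg); 0.26/220 = 0.12 (8 mg); 0.09/110 = 0.08 (placebo).
- Rate r in every arm, none truly responding. The overstated difference is (active rate - placebo rate) × r:
  - 12 mg: 0.31 × 0.005 = 0.16 to 0.31 × 0.03 = 0.93 points.
  - 8 mg: 0.17 × 0.005 = 0.09 to 0.17 × 0.03 = 0.51 points.
- If unblinding occurred only on active drug, the placebo term drops out. At r = 3% the figures become 0.40 × 0.03 = 1.2 points and 0.26 × 0.03 = 0.78 points.

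The planned differences are 40 - 9 = 31 and 26 - 9 = 17 points. The bias figures ignore that imputation also conditions on earlier SALT. That would usually pull a patient who was not responding before the exit below the arm average, so they lean high.

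**The case against.** The best defence is that 8.4 is a deliberate, narrow exception. Section 8.3 states an intent, 8.4 says should, and 8.3 itself foresees patients who are withdrawn by others. Blinding matters here. Section 7.3 says "All study patients, Investigators, and site study staff will be blinded to study drug assignment for the duration of the study", SALT is scored live and preferably by one rater throughout (10.2), scalp photographs get no formal analysis (10.3), and SPRO, the first key secondary endpoint, is the patient's own rating. Declining to use ratings made with knowledge of treatment is a reasonable trade, and continued visits would bring some into the data. All of this stands. It explains why an exception might be wanted. It does not explain why laboratory and safety visits should end too, and the protocol does not make the argument.

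Three stronger readings are tempting, and the documents do not support them:

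- A reader might infer that 8.4 breaches the estimand. The strategy in 12.4.2 is stated for discontinuation of treatment; unblinding is not a listed intercurrent event. Section 8.4 creates missing data under that strategy but breaks no stated rule.
- A reader might infer that safety follow-up of the event stops. Under 11.3 adverse events are followed as long as needed to judge safety, 11.5 records them to the final study visit, and 11.6 carries serious events through the safety follow-up visit where one applies.
- A reader might infer that the primary result or its power is at risk. The figures above show otherwise.

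The two manuals named in 8.4 are not available, so they may hold a rationale or follow-up steps.

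**Conclusion.** The point holds as an unexplained departure from the protocol's own retention intent that costs follow-up data for no stated gain. The loss is chiefly scheduled safety, laboratory and endpoint assessments in a small group selected by an adverse event. The effect on the primary estimate is very small: below one point for either dose with equal unblinding rates up to 3%, and about one point at most if only active arms are affected. Those figures rest on an assumed rate and on every such patient being a true non-responder. Power stays in line with the stated values, and the tipping-point analysis already covers these patients.

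The reason to act is that the change is cheap and leaves more options. With follow-up and a flag, the analysis can be run with or without ratings made after unblinding; after withdrawal it cannot be run with them.

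Section 8.4 is not the only such text. Protocol 9.5 requires study withdrawal for prohibited medication, while 8.3 lists the same event as a reason to stop treatment only. Both allow short-term use in some circumstances. There the mismatch concerns a single event and cannot be explained by blinding.

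**What to change.** - **Protocol 8.4:** replace withdrawal from the study by wording such as *discontinued from study drug, with scheduled visits, safety follow-up and endpoint collection continuing to Week 24 under Section 8.3 unless consent is withdrawn*.
- **Protocol 9.5:** make the same edit for prohibited medication, so that it agrees with 8.3.
- **Data:** flag the unblinding and its date.
- **SAP:** run the primary and SPRO analyses with and without assessments made after the flag, setting those assessments to missing in the second run.

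The cost is two short text edits, one data flag and one extra run. The downside is that a few later SALT, CGI and SPRO ratings may be made with knowledge of treatment; the flag identifies them and the second run shows the result without them. If the sponsor prefers withdrawal, 8.4 should say that it is an exception to 8.3 and give the reason, and the SAP should state how these patients are classed in Sensitivity 1.
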